1.3.5 Predicting ECT-Induced Cognitive Impairment through Multi-Scale Entropy

Additional data from our group suggests that resting EEG can be used to predict cognitive adverse effects following a course of seizure therapy. We obtained resting-state EEG from 34 patients receiving MST or ECT, and employed multi-scale entropy to quantify the complexity of brain temporal dynamics before and after seizure therapy. Temporal complexity represents the temporal fluctuations in resting state neurophysiological signals. The more complex the signal, the less recurring temporal patterns it contains. In ECT, but not MST, complexity of brain temporal dynamics in coarse time scales was significantly increased. In a subset of 19 patients we obtained scores of global cognitive function using the Montreal Cognitive Assessment (MoCA)[70] before and after ECT (n = 6) and MST (n =13) treatment. We found that increased complexity in coarse time scales derived through multi-scale entropy from EEG predicted change in MoCA with over 90 percent accuracy.

1.4.1 Specific Aims

The specific aims of this proposal are: (1) to conduct a randomized non-inferiority trial evaluating the efficacy, tolerability and cognitive adverse effects of two different forms of convulsive therapy for depression, (2) to assess the efficacy of two forms of convulsive therapy in ameliorating suicidal ideation in patients with depression and (3) to identify a neurophysiological biomarker of a clinically meaningful treatment response indicator. Two of the least invasive forms of convulsive therapy will be compared: RUL-UB ECT and a novel form of convulsive therapy that uses high intensity repetitive magnetic field pulses, called MST. MST has been shown to have

similar efficacy to RUL-UB ECT with minimal cognitive adverse effects. Pilot data from our naturalistic study of MST in 70 patients with depression demonstrates strong evidence for MST treatment efficacy. Our data also demonstrates that MST produces significant remission of suicidal ideation and minimal cognitive adverse effects.

Biomarkers of convulsive therapy response could further improve treatment efficiency and efficacy by identifying the patients who are most likely to benefit from these treatments. In this regard, we have developed a promising neurophysiological biomarker– cortical inhibition - that can predict treatment response through remission of suicidal ideation following a course of MST with 90 percent sensitivity and specificity.

Overall, this proposal will have transformative real-world clinical impact if MST demonstrates non-inferior efficacy compared to RUL-UB ECT. Healthcare providers, patients and policy makers would consequently demand this form of convulsive therapy. This is because only 1% of patients with depression accept a course of ECT owing to the cognitive adverse effects and negative stigma associated with ECT [4, 5]. A more acceptable and cognitive sparing form of convulsive therapy is desperately needed for patients with depression. Finally, the development of a reliable biomarker to guide response prediction will help identify those patients who are most likely to benefit from convulsive therapies.

2.0 RISK/BENEFIT ASSESSMENT

2.1.1 Known Potential Risks

Based on safety studies over the last decade the known risks of the magnetically-induced seizures of MST are not greater than the known risks of electrically-induced seizures in ECT [71] and these are summarized below. The most likely additional risk with MST would be the risk of a missed seizure. However, missed seizures have a very low rate of occurrence from our CAMH open-label trial (i.e., <1/100 treatments). If the patient has clinically significant suicidal ideation with imminent intent or attempted suicide and requires hospitalization then [name] at CAMH, [name] at UT Southwestern or [name] at UCSD will be notified and the patient will be seen and assessed to determine the most appropriate plan of care. Patients may experience side-effects after each MST treatment. This can be caused by the treatment itself, the anesthetic medication, or not having anything to eat or drink for a long period of time. The most common side-effects are headache, dizziness, nausea or vomiting, muscle aches and fatigue. Treatment is available and will be provided by medical staff in the event of study-related injury or adverse event.

Known Risks of Seizure Therapies (ECT/MST) include:

- 1) Risks of general anesthesia, which involves about 1/100,000 treatments risk of death.
- 2) Risks of non-terminating seizures in about 1/100. This is usually treated with a medication given to the patient by the doctor monitoring the anesthesia.
- 3) Risks of decreased heart rate in about 1/100. This usually resolves on its own, but is monitored.
- 4) Risks of high blood pressure in about 1/100. This usually resolves on its own but is monitored. The anesthetist may also administer a fast-acting medication to reverse severe high blood pressure.

- 5) Risks of increased brain pressure in about 1/100,000. This effect, again, is usually temporary, and patients with conditions that would increase this risk are identified during the initial ECT screening.
- 6) Risks of temporary decline in blood oxygen during the seizure. Again, this is usually temporary and is monitored throughout the duration of the seizure.
- 7) Risks associated with a confusional state, including agitation and risk of injury due to falls from the ECT bed following the seizure. This is minimized by close supervision. In rare cases, brief sedation is used to avoid fall/injury.
- 8) Risks of emergence of hypomanic or manic symptoms. Emergent hypomanic or manic symptoms is possible with any antidepressant therapy. A measure of manic symptoms (see Section 5.1.5) is included in the weekly assessments to monitor and document the presence or absence of hypomanic or manic symptoms.
- 9) Risk of suicidal or depressive symptom worsening: There will be a psychiatrist available to our study participants. In addition, our participants will be notified that in the event of serious symptom worsening they should visit the respective study site's ER or another ER that is closer in proximity to receive immediate care.

2.1.2 Known Potential Benefits

The potential benefits of the proposed research include: 1) a significant decrease in suicidal ideation and depressive symptoms, 2) significantly fewer memory impairments with MST compared to ECT, 3) faster recovery or orientation immediately following treatment with MST versus ECT. Our preliminary data suggests response rates of over 50 percent and extensive research on ECT has illustrated a remission rate of between 50-75 percent.

2.1.3 Safety of TMS-EEG

EEG recordings are not associated with any known risks to health and there is no evidence that there are either short-term or long-term side effects though some scalp discomfort during the procedure which can occur in a small proportion of patients.

Magnetic stimulators capitalize on the ability of time-varying magnetic fields to induce eddy currents in biologic tissue via the principle of electromagnetic induction. The magnetic stimulator stores electrical current and then discharges it in brief pulses through a stimulating coil. A magnetic field forms around the coil; with the magnetic flux lines perpendicular to the current flow. When the resultant magnetic field is applied to a conducting medium, such as nervous tissue, an electrical current is induced in that medium that results in neuronal depolarization. This technique has been used to stimulate peripheral nerves and the central nervous system and has now become a tool for clinical neurophysiology. The ability of TMS to non-invasively stimulate brain areas presents a significant advance beyond techniques that require the invasive method of direct cortical or transcranial electrical stimulation. Magnetic fields pass through scalp and skull without the impedance encountered by direct electrical stimulation, permitting enhanced control over the site and intensity of stimulation.

In numerous studies[72], single pulse TMS has been found to pose no significant health risk to properly screened healthy volunteers. Prospective studies designed to systematically evaluate

health effects have not found changes in EEG, blood pressure, heart rate, serum cortisol, serum prolactin, cerebral blood flow, memory or cognition. Single pulse TMS of the motor cortex has been used in children and infants as young as 2 weeks of age with no adverse effects reported. Single pulse TMS is now in routine clinical diagnostic use in hundreds of neurophysiological laboratories worldwide. The induced electrical current is well below that which is expected to cause harm to nervous tissue. The US FDA has concluded that stimulation at <1 Hz carries virtually no risk seizure and is therefore classified as a non-significant risk device[73].

3.0 OBJECTIVES AND HYPOTHESES

Primary objective: To assess the efficacy and cognitive adverse effects of MST compared to RUL-UB ECT in patients with depression.

Primary hypothesis/combined effectiveness endpoint: (1) MST will result in remission rates on the 24-item Hamilton Rating Scale for Depression (HRSD-24) that is non-inferior to that of RUL-UB ECT; **AND** (2) MST will have a superior cognitive adverse effect and tolerability profile compared to RUL-UB ECT as assessed with the Autobiographical Memory Test (AMT).

Secondary objective: To assess the efficacy MST compared to RUL-UB ECT in ameliorating suicidal ideation in patients with depression.

Secondary hypothesis/effectiveness endpoint: MST will have a non-inferior remission rate on the SSI compared to RUL-UB-ECT in patients with depression.

Tertiary objective: To refine and develop candidate neurophysiological biomarker, cortical inhibition (CI), using combined transcranial magnetic stimulation and electroencephalography (TMS-EEG) that may predict response to treatment using remission of suicidal ideation as a meaningful clinical indicator.

Tertiary hypothesis/effectiveness endpoint: (1) Change in CI in the DLPFC following MST will significantly predict SSI reduction; (2) Following MST and ECT, increased complexity in course time scales derived through multi-scale entropy will be associated with change in the AMT scores in patients with depression.

4.0 SIGNIFICANCE

An alternative first-line convulsive therapy with high remission rates in severely ill patients and those with treatment resistance would be transformative for the field. Novel pharmacotherapies and other neurostimulation treatments such as rTMS only yield remission rates around 30% leaving a significant proportion of patients struggling with persistent symptoms. Yet, few accept ECT because of the negative stigma and cognitive adverse effects despite an impressive remission rate that is nearly double all other treatments for TRD. The results of this RCT could have significant impact on the treatment of depression. First, if MST demonstrates comparable efficacy to ECT, but without its cognitive adverse effects, it should be rapidly adopted into clinical practice as providers, patients and their families will likely accept this treatment. During our

open-label pilot clinical trial, patients were much more open to the idea of convulsive therapy if the cognitive adverse effects were known to be lower. Thus, the improved cognitive profile of MST will certainly lead to improved treatment acceptability. Fortunately, ECT suites can easily accommodate MST without major modifications. Reduced duration of post-treatment disorientation will substantially improve patients' experience and minimize their time in the clinic. By establishing MST as a safe and effective treatment for severe depression, this trial will advance the care of depression—a disabling illness for which there are few alternatives.

5.0 APPROACH

5.1.1 Research Design and Methods

The trial will be registered in an international clinical trial registry (clinicaltrials.gov) and results will be reported in a manner consistent with the international CONSORT guidelines. The study will involve a randomized, double blind, parallel-group clinical trial with two treatment arms conducted at three leading academic institutions in North America: CAMH, University of Texas Southwestern in Dallas, and University of California, San Diego (UCSD). Based on our power analysis (Section 5.7.1), a total of 260 participants with depression will be randomized to receive MST or RUL-UB-ECT. We plan to enroll four to five participants per month across the three study sites over 54 months.

Treatment will be administered two to three days per week. Depression symptoms will be assessed with the 24-item Hamilton Depression Rating Scale (HRSD-24) [74] and suicidality will be assessed with the Scale for Suicidal Ideation (SSI) [69]. Remission will be defined as HRSD-24 ≤ 10 and a $> 60\%$ decrease in scores from baseline on two consecutive ratings. Once a participant reaches remission, a second rating to confirm remission will be conducted immediately before their next scheduled treatment. If remission is confirmed, they will then be considered a completer of the acute treatment course. Remission of suicidal ideation is defined as a score of 0 on the SSI. Therefore, there will be no specific minimum number of treatments that patients must receive to be classified as remitters. However, patients who do not meet remission criteria after 21 treatment sessions will be considered non-remitters and will cease treatment sessions. This maximum treatment number was chosen allowing for the possibility that MST may require more treatment sessions to achieve remission, similar to RUL-UB ECT [29-31]. The blind will not be broken to participants until the completion of the entire study. Following completion of the acute treatment course, participants who achieve response (defined as a 50% reduction in symptoms on the HRSD-24 from baseline) or remission will be referred to a maintenance treatment trial.

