5.1.2 Subjects

Inclusion Criteria

Patients will be included if they:

- (1) are inpatients or outpatients;
- (2) are voluntary and competent to consent to treatment and research procedures according to ECT/MST attending psychiatrist (Section 5.1.4);
- (3) have a MINI International Neuropsychiatric Interview diagnosis, Version 6 (MINI-6.0) diagnosis of non-psychotic MDD

- (4) are 18 years of age or older
- (5) have a baseline HRSD-24 score ≥ 21 ;
- (6) are considered to be appropriate to receive convulsive therapy as assessed by an ECT attending psychiatrist and a consultant anesthesiologist
- (7) are agreeable to keeping their current antidepressant treatment constant during the intervention;
- (8) are likely able to adhere to the intervention schedule;
- (9) meet the MST safety criteria [75];
- (10) If a woman of child-bearing potential: is willing to provide a negative pregnancy test and agrees not to become pregnant during trial participation.

Exclusion Criteria

Patients will be excluded if they:

- (1) have a history of MINI diagnosis of substance dependence or abuse within the past three months;
- (2) have a concomitant major unstable medical illness;
- (3) are pregnant or intend to get pregnant during the study;
- (4) have a MINI diagnosis of any primary psychotic disorder
- (5) have a MINI diagnosis of obsessive compulsive disorder, or post-traumatic stress disorder deemed to be primary and causing more functional impairment than the depressive disorder
- (6) have probable dementia based on study investigator assessment;
- (7) have any significant neurological disorder or condition likely to be associated with increased intracranial pressure or a space occupying brain lesion, e.g., cerebral aneurysm;
- (8) present with a medical condition, a medication, or a laboratory abnormality that could cause a major depressive episode or significant cognitive impairment in the opinion of the investigator (e.g., hypothyroidism with low TSH, rheumatoid arthritis requiring high dose prednisone, or Cushing's disease);
- (9) have an intracranial implant (e.g., aneurysm clips, shunts, stimulators, cochlear implants, or electrodes) or any other metal object within or near the head, excluding the mouth, that cannot be safely removed;
- (10) require a benzodiazepine with a dose > lorazepam 2 mg/day or equivalent or any anticonvulsant due to the potential of these medications to limit the efficacy of both MST and ECT;

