5.8.2 Secondary Outcome Analysis

Our secondary effectiveness endpoint outlines that MST will have a non-inferior remission rate on the SSI compared to RUL-UB-ECT in patients with depression. Our sample size calculation of 260 subjects was based on non-inferiority trial calculations that are sufficient to minimize Type II error[103] and are consistent with prior NIMH sponsored ECT trials[27]. RUL-UB-ECT and MST can achieve remission in approximately 60% of TRD patients [28, 92].

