5.8.4 Tertiary Outcome Analysis: Neurophysiological Data

We will investigate the relationship between change in CI and SSI reduction by calculating the area under the receiver operating characteristic (ROC) curve (AUC) as discussed above (Section 1.3.4). ROC analysis is used in medicine to evaluate diagnostic test accuracy. The ROC involves plotting the sensitivity (true positive rate) versus 1-specificity (false positive rate). The ROC AUC predicts performance of the diagnostic test. An AUC of 1 represents perfect prediction with optimal sensitivity and specificity while 0.5 suggests that the diagnostic test is no better than chance at diagnostic prediction. For our purposes, the ROC AUC then corresponds to the change in CI that optimally distinguishes MST and ECT remitters from non-remitters (defined as a zero score on the SSI). Based on our preliminary data described above (Section 1.3.4), we will use change in CI (defined as the LICl TMS-EEG response) to distinguish MST and ECT SSI remitters from non-remitters using a ROC AUC of >0.85 on all frontal electrodes using a false detection rate correction that is applied to all frontal electrodes.

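### Suicidal-ideation remission is a bare SSI score of 0 and entry does not require ideation, so participants at 0 throughout count as remitters and shrink the secondary non-inferiority difference

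*Combined protocol and SAP*

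**What the plan says.** All references are to the combined protocol and SAP.

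- **Definition (Section 5.1.1).** "Remission of suicidal ideation is defined as a score of 0 on the SSI". It requires no change from baseline and no baseline score above 0. In the same paragraph, HRSD-24 remission needs a score of 10 or less and also a more than 60% "decrease in scores from baseline on two consecutive ratings".
- **Eligibility (Section 5.1.2).** The only severity threshold is that patients "have a baseline HRSD-24 score ≥ 21". None of the 10 inclusion or 12 exclusion criteria mentions the SSI or suicidal ideation.
- **Secondary hypothesis (Section 3.0, repeated in Section 5.8.2).** "MST will have a non-inferior remission rate on the SSI compared to RUL-UB-ECT in patients with depression". The population is not limited to those with ideation.
- **Secondary analysis (Section 5.8.2).** "Our sample size calculation of 260 subjects was based on non-inferiority trial calculations that are sufficient to minimize Type II error", followed by "RUL-UB-ECT and MST can achieve remission in approximately 60% of TRD patients". The section gives no SSI margin, test, analysis set or handling of baseline score.
- **Tertiary analysis (Section 5.8.4).** The remitter label for the ROC analysis is again "defined as a zero score on the SSI".
- **Data available (Section 5.1.5 and Appendix A, Table 1).** The SSI is collected at baseline visit V1.

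**The concern.** The secondary objective is to learn whether MST relieves suicidal ideation as well as ECT does. A participant with no ideation at entry cannot contribute to that question, yet the rule scores such a person as a success if the SSI is still 0 at the end. These successes should be about equally common in both arms, because randomisation balances baseline score. They raise both remission rates and dilute any real difference. In a superiority test that would be conservative. In a non-inferiority test it works in favour of the claim.

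The HRSD-24 endpoint is protected twice, by an entry threshold and by a required percentage fall. The SSI endpoint has neither protection. In the ROC analysis, the same participants carry a remitter label that treatment did not produce.

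**Working it through.** **1. The plan's sample size.** For non-inferiority of two proportions with equal true rates p, margin m and unpooled variance:

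n per arm = 2p(1 − p)(z₀.₉₅ + z₀.₈₀)² / m², with (1.645 + 0.842)² ≈ 6.183 and m = 0.15.

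- p = 0.60 (the rate in Section 5.8.2): 0.48 × 6.183 / 0.0225 = 131.9, so 132 per arm, 264 in total. Power at 130 per arm is 79.5%.
- p = 0.50 (the rate in Section 5.7.1): 0.50 × 6.183 / 0.0225 = 137.4, so 138 per arm, 276 in total. Power at 130 per arm is 78.0%.

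So 260 corresponds closely to 80% power with a 15-point margin at one-sided 0.05, provided all 130 per arm can contribute.

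**2. Inputs for the dilution check.**

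- From the plan: 130 per arm (Section 5.7.1).
- Borrowed from Stage 1 (Section 5.8.1), because no SSI values are given: 15-point margin, one-sided Z-test at 0.05.
- Assumed: remission among those with baseline SSI above 0 is 60% on ECT and 45% on MST, a deficit equal to the margin. The 60% is the figure in Section 5.8.2, which does not say that it is an SSI rate.
- Assumed, with a range: the share q at SSI 0 at baseline who stay at 0.

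**3. Dilution.** Each arm's rate is q + (1 − q)p, so the overall difference is (1 − q)(p_ECT − p_MST).

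Example at q = 20%: ECT 0.20 + 0.80 × 0.60 = 0.68; MST 0.20 + 0.80 × 0.45 = 0.56; difference 0.12. SE = √[(0.68 × 0.32 + 0.56 × 0.44)/130] = 0.0597. P(declare non-inferiority) = Φ[(0.15 − 0.12)/0.0597 − 1.645] = Φ(−1.14) ≈ 12.7%. The exact binomial value is 12.3%.

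| q | ECT / MST overall | Difference (points) | P(non-inferior), exact | Subset deficit that equals 15 points overall |
|---|---|---|---|---|
| 0% | 60.0 / 45.0% | 15.0 | 5.2% | 15.0 |
| 10% | 64.0 / 50.5% | 13.5 | 8.1% | 16.7 |
| 20% | 68.0 / 56.0% | 12.0 | 12.3% | 18.8 |
| 30% | 72.0 / 61.5% | 10.5 | 19.4% | 21.4 |
| 40% | 76.0 / 67.0% | 9.0 | 28.5% | 25.0 |

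The last column is 15/(1 − q). A simulation of 200,000 trials per q agrees with the exact values to within about 0.1 point. If only 90% of the baseline zeros stay at 0, the normal-approximation figures are 8.1, 12.6, 18.8 and 27.2% at q = 10 to 40%, so the conclusion barely moves.

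**4. After restricting to baseline SSI above 0.** With 130(1− q) per arm and 60% v 45%, P(non-inferior) is about 5% at every q. With equal 60% rates, power is:

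| q | Analysed per arm | Power, exact | Power, normal approx. | Randomised per arm for 80% |
|---|---|---|---|---|
| 10% | 117 | 77% | 75.7% | 147 |
| 20% | 104 | 71% | 71.3% | 165 |
| 30% | 91 | 66% | 66.3% | 189 |
| 40% | 78 | 60% | 60.5% | 220 |

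The last column is 131.9/(1 − q), rounded up.

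**5. What the 60% might mean.** If it already includes people at 0 from the start, the rate among those with ideation is (0.60 − q)/(1 − q): 55.6, 50.0, 42.9 and 33.3% at q = 10, 20, 30 and 40%. The plan does not say which is meant.

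**The case against.** Four points can be made against this.

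- **The plan nowhere says that baseline zeros count.** True. Section 5.8.2 names no analysis set, and remission normally implies something to remit from. The counting follows from a bare definition, open eligibility and the absence of any restriction. It would be too strong to say that the sponsor chose to count these participants, but a programmer following Section 5.1.1 would count them.
- **It is an error only under one estimand.** If the target is the proportion at SSI 0 among all patients with depression, a true 12-point deficit lies inside a 15-point margin and declaring non-inferiority is correct. This stands: the percentages above are error rates only if the margin applies to people with ideation. That target fits the stated objective of relieving ideation better, but the plan does not settle it.
- **The size is unknown.** This stands. The documents give no q, and patients considered for convulsive therapy may seldom score 0.
- **The ROC analysis is partly protected.** The tertiary hypothesis in Section 3.0 concerns reduction in SSI, which refers to baseline. But Section 5.8.4 carries it out with the zero-score label, so the ambiguity remains there. No size is claimed for that effect.

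A reader might also infer that the plan claims 80% power for the SSI endpoint and is wrong. It does not: the 80% in Section 5.7.1 is for HRSD-24 remission, and Section 5.8.2 says only that 260 is enough.

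**Conclusion.** The point holds as a defect in the secondary endpoint's definition. The stated rule credits remission to participants who had no ideation, and the direction of the effect is towards non-inferiority. Under the borrowed margin and level and the assumed 60% v 45%, the chance of declaring non-inferiority despite a 15-point deficit among those with ideation rises from about 5% at q = 0 to 8, 12, 19 and 29% at q = 10, 20, 30 and 40%. All of those inputs except the 130 per arm are assumptions for the SSI endpoint.

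The documents do not support the inference that the trial's main conclusion is at risk: neither HRSD-24 remission nor the AMT uses the SSI. Nor do they show that the effect is large in this population. It is a correction that should be made before unblinded analysis, because a denominator chosen afterwards would be open to the charge of being data-driven.

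**What to change.** In Sections 5.1.1, 5.8.2 and 5.8.4:

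1. Define SSI remission as an SSI of 0 at the end of acute treatment among participants whose baseline SSI is above 0, with the same analysis-set convention as Stage 1. Use the same subset for the remitter label in the ROC analysis.
2. Report the proportion at SSI 0 among all participants as a supportive analysis.
3. State the SSI non-inferiority margin.
4. Replace the statement that 260 suffices with the precision or power expected in the ideation subset, using the sponsor's own estimate of q.

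The baseline SSI is already collected, and restricting on a pre-treatment score does not in itself disturb the randomised comparison, so trial conduct does not change. The cost is fewer analysed participants and lower power for the secondary endpoint: about 77, 71, 66 and 60% at q = 10, 20, 30 and 40% under the assumptions above. Restoring 80% would take about 147 to 220 randomised per arm over that range. Reporting the lower power openly is the cheaper course.
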